**Inclusion criteria:**

1) Males and females, between the ages of 21 and 65; 2) Non-treatment seeking individuals with current DSM-5 AUD (please note we will exclude those with physiologic dependence on alcohol). This will be determined by the study physician conducting the physical examination, and by the Clinical Institute Withdrawal Assessment for Alcohol Scale (CIWA-Ar)[64] with those with score of  $\geq 8$  excluded; 3) No current substance use disorder (except tobacco, alcohol, and marijuana); 4) No current medical problems and normal ECG; 5) For women, not pregnant as determined by pregnancy screening, not breast feeding.

**Exclusion criteria:**

1) Current major psychiatric illnesses including mood, psychotic, or anxiety disorders; 2) History of major medical illnesses; including liver diseases, heart disease, chronic pain or other medical conditions that the physician investigator deems contraindicated for the subject to be in the study; 3) Liver function tests (ALT or AST) greater than 3 times normal; 4) weight  $> 120\text{kg}$ ; 5) renal impairment; and 6) patients on the following medications: a) medications for alcoholism (e.g. naltrexone, disulfiram, topiramate, acamprosate); b) psychotropic medications that promote sedation (please note patients on psychotropic medications for current psychiatric conditions will also be excluded); and c) patients currently taking antibiotics or antifungals.

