**Neurosteroids in alcohol drinking behavior and AUD:** A substantial body of preclinical and human studies show that neuroactive steroids have a role in alcohol reinforcement, tolerance, dependence and withdrawal. Data also indicates that neurosteroids, and ALLO in particular, may have significant therapeutic potential in AUD because of their ability to normalize a dysregulated HPA axis response typically found in chronic alcohol abuse. **A2a.** *In preclinical studies:* Alcohol increases the levels of progesterone (PROG) and ALLO in alcohol-preferring and non-preferring rats [13-15]. Administration of ALLO increases alcohol self-administration in non-dependent rats and in non-dependent alcohol-preferring rats. However, chronic ethanol consumption in rats leads to decreases in plasma neurosteroid release [16-18], and decreased levels of ALLO after reintroduction of alcohol in alcohol-withdrawn animals[19]. Similarly, female monkeys who drink excessively tend to experience disruptions in their menstrual cycle, putatively due to neurosteroid depletion and low levels of ALLO [20]. *Rodents who consume high doses of alcohol for long periods of time show decreases in alcohol consumption after a single infusion of ALLO [19, 21] suggesting ALLO may play an important compensatory role in mediating alcohol effects.* **A2b.** *In healthy humans:* Similar to preclinical studies in healthy humans: a) alcohol intoxication increases plasma levels of ALLO [22, 23], b) ALLO levels are correlated with levels of intoxication [22, 23] and subjective effects (“liking” or “wanting” more alcohol)[24], c) pretreatment with finasteride (reduces the formation of ALLO and PROG) blocks subjective stimulant effects of alcohol[24] and reduces drinking in men[25], and a single dose of dutasteride attenuates subjective sedative effects in non AUD men [26], d) women are less sensitive to the effects of alcohol and drink more during the follicular phase of their cycle, when ALLO levels are at their lowest [27]. There are some negative studies that show no relationship between intoxication and ALLO levels at lower doses of alcohol [28], in women in the follicular phase[29] or the luteal phase [30], and find lower levels of PROG and ALLO after alcohol administration [31]. **A2c:** *In humans with AUD:* Mirroring preclinical studies, women who drink excessively tend to experience disruptions in their menstrual cycle presumably due to neurosteroid depletion and lower levels of ALLO[32]. Dysregulation in HPA axis function has been reported in individuals with AUD while they are actively drinking, during withdrawal, and during abstinence [33-35]. Also, suppression of neurosteroid release has been reported in individuals with AUD as well as their relatives after administration of naloxone [35, 36]. A recently published study examined the effect of progesterone stimulated ALLO in cocaine dependent men and women on stress-induced craving, mood, and cognitive functioning. High levels of ALLO were associated with decreased craving, increased mood ratings, and improved cognitive performance suggesting ALLO may have important therapeutic utility in addiction. *In conclusion, data from animals and humans show that ALLO may have a significant therapeutic potential although there are no studies to date that examine the role of ALLO administration in AUD.*

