## 5. Research Plan:

**A. Our experience with laboratory stress-induced paradigms:** In a recent, randomized, within-subjects laboratory study, we compared the effects of neutral and stress cues (presented

**Overview:** This is a double-blind, placebo-controlled, between-subjects study with 1 test day. Subjects will receive intravenous ALLO infusion to achieve a targeted plasma (100 nM; N=30, n=15 men, 15 women) or placebo (PLA; N=30, n=15 men, n=15 women) in a randomized fashion. We recognize that the double-blind in the study may be compromised by the lack of an active placebo. However, ALLO side effects or their intensity have not been extensively studied at this dose. The dose of alcohol is also so low that possible side effects of alcohol are also very slim. In addition, our group has extensive experience conducting similar studies where, for example, high dose of alcohol (significantly higher than in this study) is compared to a placebo. In order to protect the blind for the participants we have combined the possible side effects for ALLO, alcohol and placebo. For each subject, the rate of infusion will be calculated based on their weight. After 60 min. of infusion, participants will be exposed to 2 conditions in random order: stress cues and neutral cues. The cues will consist of a 5 min. presentation of the stimulus (stress or neutral) followed by immediate evaluation of craving and anxiety. There will be a relaxation procedure between each condition (see Table in Human Subjects section), and the presentation of the second cue will be initiated after stress levels have decreased to baseline. During the first hour of infusion and before the start of the stress paradigm, all participants will complete a number of measures to characterize ALLO's effects on mood, cognitive performance and motor coordination. Following the script presentations all participants will receive IV alcohol (40 mg%) that will be infused over 20 min and clamped at a steady level for an additional 30 min (Study procedures are also presented in tabular form in the Human Subjects section). All subjects will make 2 visits, one to develop the scripts and one for testing. In order to control for baseline differences in ALLO we will study women in their follicular phase of the menstrual cycle when levels of ALLO are most stable. In the follicular phase, women have low ALLO levels that are comparable to those in men, < 1 nmol/L [61]. Women have higher ALLO levels than men in the luteal phase (> 4 nmol/L), and especially high during pregnancy (100 to 160 nmol/L)[62]. For females, all sessions will be scheduled within the first 4-7 days of a woman's menstrual cycle.

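### The excluded-medication list does not name finasteride or dutasteride, which the protocol's own background says alter the alcohol effects measured in primary Aim 1c

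*Combined protocol and SAP*

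**What the plan says.** Exclusion criterion 6 (section 5, Exclusion criteria) lists three groups of medication:

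- (a) "medications for alcoholism (e.g. naltrexone, disulfiram, topiramate, acamprosate");
- (b) sedating psychotropics, and any psychotropic taken for a current psychiatric condition;
- (c) "patients currently taking antibiotics or antifungals".

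Finasteride and dutasteride belong to none of these and appear in no other eligibility text.

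The Background and Significance section, in its paragraph on healthy humans, reports that "pretreatment with finasteride (reduces the formation of ALLO and PROG) blocks subjective stimulant effects of alcohol" and that "a single dose of dutasteride attenuates subjective sedative effects in non AUD men". Aim 1c, one of the primary aims in section 2, is that ALLO attenuates the stimulant and sedative effects of alcohol on the BAES.

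Two other criteria bear on entry. Inclusion criterion 4 requires "No current medical problems and normal ECG", and exclusion criterion 2 gives the physician discretion over medical conditions.

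For women, the Overview in section 5 states: "In order to control for baseline differences in ALLO we will study women in their follicular phase".

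**The concern.** The protocol identifies two drugs that act on the pathway under test and change what a primary endpoint measures, then leaves both off its list of excluded drugs. The criteria that might catch users concern conditions, not medications. A man taking one of these drugs without a condition that the physician counts as a current medical problem can qualify.

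Nothing later in the plan compensates:

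- Randomization is stratified by gender only.
- The mixed model in section 5.D has no term for concomitant medication.
- Plasma ALLO is to be related to mood, cognition, motor coordination, craving and anxiety, but not to the BAES.
- Table 2 lists no ALLO sample between +55 and +150 minutes, so none while alcohol is running (+70 to +120 minutes).
- The Overview puts men's ALLO below 1 nmol/L to begin with, so a baseline sample may not reveal a user.

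At stake is some loss of sensitivity on Aim 1c, and a source of variation that cannot be separated out afterwards if nobody asked about it.

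**Working it through.** **Inputs from the documents.** 30 completers per arm, planned as 15 men and 15 women (section 5, Overview). Two-sided alpha is 0.05. The plan claims at least 80% power, with d = 0.74 for ALLO against placebo and f = 0.5 for the Aim 1 interactions (section 5.D).

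**Input not in the documents.** The share of enrolled men using either drug. I vary it from 1 user among 30 men to 20% of men.

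**Step 1: reproduce the plan's figure.** Two-sample t test, noncentrality = d / √(2/n) = 0.74 / √(2/30) = 2.87, with 58 degrees of freedom. Power is 0.805, and the effect detectable at 80% power is d = 0.736. The stated 0.74 is reproduced. At f = 0.5, with 1 numerator degree of freedom and N = 60, power is 0.968, so the claim of at least 80% also holds there.

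**Step 2: dilution.** Suppose k of the 60 participants are users, spread evenly over the arms, and show no ALLO-placebo difference on the BAES. Then d_all = 0.74 × (1 − k/60). Added variance is ignored.

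| Users among 30 men | d_all | Power |
|---|---|---|
| 0 | 0.740 | 0.805 |
| 1 | 0.740 × 59/60 = 0.728 | 0.791 |
| 2 | 0.740 × 58/60 = 0.715 | 0.778 |
| 3 (10%) | 0.740 × 57/60 = 0.703 | 0.763 |
| 6 (20%) | 0.740 × 54/60 = 0.666 | 0.718 |

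If users keep half the effect, three users give d_all = 0.74 × (1 − 0.5 × 3/60) = 0.722 and power 0.785. If the true effect is as large as f = 0.5 (d = 2f = 1.0), one user moves power from 0.968 to 0.963 and three users to 0.951.

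**Step 3: balance between arms.** Stratification by gender balances users in expectation only. With two users among 30 men, 15 per arm, the chance that both fall in the same arm is 14/29 = 48%.

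**Step 4: gender comparison.** Under the Step 2 assumptions, a share s of users among men creates an apparent gender gap of 0.74 × s: 0.04 SD at 5%, 0.07 at 10% and 0.15 at 20%. The standard error of the gender-by-drug contrast with 15 per cell is √(4/15) = 0.52 SD. The gap is small beside it.

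**The case against.** The strongest reply is that the omission is real but its consequences are uncertain and probably small. Much of that stands.

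- **Evidence base.** The background places these findings in healthy subjects, and for dutasteride in men without alcohol use disorder (AUD), whereas every participant here has AUD. Each drug is documented for one BAES dimension only. The same paragraph reports negative studies on intoxication and ALLO levels at lower alcohol doses, and the protocol describes its own dose as low. The title of the finasteride study speaks of attenuation, so full blocking is an upper bound.
- **Existing safeguards.** The medical history, the requirement of no current medical problems and physician discretion narrow entry. They do not close it.
- **Direction.** A reader might infer that users bias Aim 1c towards no effect, because a placebo user with a blunted response resembles a treated participant. The documents do not support that. Users are balanced in expectation, and nothing says how an ALLO-lowering drug behaves during a 100 nM infusion. If the response of a user in the ALLO arm were blunted further, the contrast would widen.
- **Share lost per user.** A reader might also take one fully blocked placebo man as removing 1/15 of the contrast in men, or 1/30 overall. Those fractions are shares of the placebo-arm mean response. For a single placebo user they equal shares of the contrast only if ALLO abolishes the response altogether.
- **Gender.** Because the two drugs would be used by men, Aim 4 might seem distorted. The induced gap is negligible against its standard error, and Aim 4 is exploratory.
- **Hormonal preparations in women.** Extending the point to these is tempting, given the follicular-phase rule. That rule addresses luteal levels above 4 nmol/L, and the background does not report that such preparations block alcohol's effects.

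**Conclusion.** The point holds as an inconsistency between the background and the exclusion list, with a modest possible effect on one primary aim. Users who enter could add heterogeneity and attenuate the Aim 1c contrast. One or two users among 30 men would cost about 1 to 3 percentage points of power at d = 0.74, and three would cost about 4.

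These figures assume that users contribute no drug effect and are spread evenly over the arms. The number of users is itself an assumption, since the documents give none. The losses are smaller if users keep part of the effect or if the true effect is near f = 0.5. No direction of bias is established, and no material effect on the gender comparison is shown. The case for acting is that the remedy is very cheap and that exposure is hard to reconstruct later if it is never asked about.

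**What to change.** Reconcile the exclusion list with the background. Add current or recent use of 5-alpha-reductase inhibitors (finasteride, dutasteride) to criterion 6, and add a matching question at screening. The investigators should define what counts as recent. One of the cited studies concerns, by its title, former finasteride users, which is a reason not to ask about current use alone.

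If the sponsor prefers not to exclude users, the minimum is to record use at screening for every participant and to pre-specify in section 5.D a sensitivity analysis of Aim 1c that omits them.

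The cost is one line of eligibility text, one screening question and an occasional extra screen failure. The sensitivity-analysis route costs no enrolment but leaves the heterogeneity in the primary analysis.

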**Screening Labs:**

EKG, CBC w/differential, Chem7, LFTs, Calcium Profile, Amylase, Lipase, Free T4, TSH, GGT, Cholesterol (including LDH), PT/PTT/INR, urine toxicology, and urinalysis (routine and microscopic). **Females only:** beta HCG (blood, quantitative).

**B. Assessments:** The assessments that will be used in this study are summarized in Table 1.

**Main outcome measures:** Craving for alcohol will be assessed using the Alcohol Urge Questionnaire (AUQ), 8 items measured on a 7-point Likert scale. Anxiety will be assessed using the State Trait Anxiety Inventory (**STAI-6**) – 6 item measure designed to assess trait and state aspects of anxiety. Sedation during the stress paradigm will be measured using a Visual Analogue Scale (**VAS**) (0=not sleepy at all to 100=falling asleep). **Biphasic Alcohol Effects Scale (BAES)** [65] is a 14-item self-report adjective rating scale that will be used to measure the stimulant and sedative effects of alcohol.

**Cognitive functioning:** Little is known about the effects of ALLO on cognitive functioning. However, GABA receptor agonists have been studied extensively and are known to negatively affect cognition. The effects of ALLO on various aspects of memory have been studied in animals and the data show that ALLO impairs spatial, working, and long-term memory [66, 67]. Only one study examined the effects of ALLO administration in healthy women and found that 0.07 mg/kg of ALLO had a statistically significant but relatively minor effect on verbal memory but no effect on semantic or working memory [37]. Verbal memory will be evaluated using *The Hopkins Verbal Learning Test-Revised (HVLT-R)*. The HVLT-R is a word list learning test of verbal memory. The main outcomes for the HVLT-R are percent corrected for immediate and delayed recalls. GABAa agonists have also been shown to affect response inhibition or the ability to suppress a response in rare and irregular situations[68, 69]. We will use the **Go No-Go task** to evaluate response inhibition [70]. A series of rectangles are presented every 1150 ms and participants are instructed to press a spacebar when they see a green rectangle (=go) but refrain from pressing the spacebar when they see a blue rectangle (=no go), and to give equal importance to speed and accuracy. The primary outcome is the number of commission errors. **Motor Coordination:** The negative effects of GABAa agonists on motor coordination have been well documented and studied for decades[71]. Motor coordination will be assessed using the **Grooved Pegboard Test** (Lafayette Instrument Company). This test is a manipulative dexterity test, consisting of a board with randomly positioned slots in which subjects insert pegs. It is an eye-to-hand coordination test that has been used in research studies, including pharmacotherapy studies [72].

**Plasma ALLO:** Deidentified plasma levels of ALLO will be analyzed by [name] lab at UCDavis. Plasma samples will be obtained on multiple time points during the lab session (see Table in Human Subjects section) to examine how levels of ALLO relate to: a) mood, cognitive performance and motor coordination, and b) stress-induced craving and anxiety.

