*To evaluate the effects of ALLO administration on cognition and motor coordination:*

**Aim #3a:** to describe ALLO's effects on cognitive functioning, we will assess verbal memory using the Hopkins Verbal Learning Test-Revised (HVLT-R), and response inhibition using the Go No-Go task.

**Aim #3b:** to describe ALLO's effects on motor coordination, we will use the Grooved Pegboard Test.

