**Proposed study:** This project will investigate if pretreatment with the neurosteroid ALLO administered intravenously attenuates stress-induced craving, anxiety and subjective stimulant/sedative alcohol effects in those with AUD using a laboratory paradigm. Subjects (N=60 completers) will receive a continuous infusion of ALLO to achieve a targeted plasma level of 100nM or placebo over 200 minutes. On a single test day, after 60 min of ALLO or placebo infusion all participants will undergo laboratory testing for stress-induced craving using personalized scripts based on an index stressful life event for each subject. This technique has been shown to produce robust and reliable craving and anxiety in subjects including heavy drinkers[1], alcohol dependent individuals[2] both with and without psychiatric comorbidity (including work by our group) and, in those with other substance use disorders[3-5]. All participants will also receive alcohol administered intravenously using a clamp procedure, targeting a breath alcohol concentration (BrAc) of 40mg% (40 mg/dL). This procedure will achieve steady-state blood alcohol levels without the individual variation from oral alcohol administration. IV alcohol administration will start after the script presentation; it will be infused over 20 min. and clamped for an additional 30 min. ALLO and placebo will be identical in color, clarity and viscosity and the blind will be maintained. The collaborator ([name]) in this study has extensive experience administering ALLO infusions in individuals with seizure disorders [55, 56], and TBI (NCT01673828). In doses proposed in this study, ALLO is very well tolerated with mild sedation being the main side effect.

[figure not shown]

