subjective mood effects, cognitive functioning and motor coordination. As stated in the specific primary aims, a significant interaction between medication and stress condition with smaller differences between the stress and neutral conditions on active drug (ALLO) vs. placebo will be considered supportive of our hypothesis. **Exploratory Aims** will examine the gender-specific effects by adding gender as a between-subject factor in the models above and testing all possible interactions involving gender. All statistical testing for the primary hypotheses will be two-sided at 0.05 significance level. Post-hoc tests and analyses of secondary outcome measures will be adjusted for multiplicity using the Bonferroni correction.

**Sample size considerations:** With 30 subjects per treatment group, we have at least 80% power to detect large effects ( $f=0.5$ ) for the interactions of interest for Aims 1a, 1b, and 1c assuming alpha=0.05. We can also detect large effects for the comparisons of ALLO dose to placebo ( $d= 0.74$ ) under the same assumptions. The effects we are proposing are based on data from Timby et al. 2006 and van Broekhoven et al 2007 who reported that ALLO administration had a large effect ( $d>0.8$ ) on saccadic eye movement and sedation among healthy subjects.

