## 6. PROTECTION OF HUMAN SUBJECTS:

Human subjects: Non-treatment seeking individuals with AUD will be recruited from the New Haven area by newspaper advertisements, Craigslist, and flyers. Based on previous human laboratory studies, approximately 10 percent of the subjects who enroll in the study, meet all inclusion/exclusion criteria and are randomized are expected to either drop out or be terminated because of non-compliance with the study procedures. To meet the target sample of 60 completers, a total of 66 participants will be randomized. After the initial phone screening, potential subjects will undergo a comprehensive evaluation that is summarized in Table 1 in “Research Strategy”.

Study Procedures: Table 1 delineates the timeline for study procedures and measures that will be administered at each time point during the laboratory session.

Table 2. Study Procedures (times are approximate)

Time	Measures and Events
Baseline	Urine and BAC check, HR/BP, CIWA, TLFB, AUQ, STAI-6, VAS; BAES, NDS, DES-R, ARCI, SDAS, HVLT-R, Go no-Go, Grooved Pegboard Test, Ghrelin, NPY and ALLO levels, breakfast
-62 min	Ghrelin and NPY levels
-60 min	ALLO infusion starts
-40 min	HR/BP, AUQ, STAI-6, VAS; BAES, NDS, DES-R, ARCI, SDAS, HVLT-R, Go no-Go, Grooved Pegboard Test, ALLO levels
-20 min	HR/BP, ALLO levels
-2 min	Ghrelin and NPY levels
Stress Reactivity Condition 1 (15 min break)	
0 min	Condition 1. (Neutral or Stress) Baseline/Relaxation; BP & HR, AUQ, STAI-6, VAS
+10 min	Image period, BP & HR
+15 min	BP&HR, AUQ, STAI-6, VAS, Ghrelin and NPY levels
+20 min	Recovery period. AUQ, STAI-6, VAS
+25 min	BP&HR, AUQ, STAI-6, VAS, Ghrelin, NPY and ALLO levels

Stress Reactivity Condition 2	
+30 min	Condition 2. (Neutral or Stress). Baseline/Relaxation as described above
+40 min	Image Period as described above
+45 min	BP&HR, AUQ, STAI-6, VAS, Ghrelin and NPY levels
+50 min	Recovery Period as described above
+55 min	BP&HR, AUQ, STAI-6, VAS, BAES, NDS, DES-R, ARCI, SDAS, Ghrelin, NPY, and ALLO levels
Alcohol Infusion	
+70 min	start of IV alcohol infusion
+90 min	Target reached STAI-6, VAS, BAES, NDS, ARCI, SDAS, HVLT-R, Go no-Go, Grooved Pegboard
+118 min	Ghrelin and NPY draw
+120 min	IV alcohol infusion ends, ALLO infusion ends
+150 min	STAI-6, VAS, BAES, NDS, ARCI, SDAS, HVLT-R, Go no-Go, Grooved Pegboard, ALLO levels, Lunch

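### Go/No-Go is scored only by commission errors, which also fall when a sedated participant presses less, so the Aim 3a inhibition result could be misread unless go-trial omissions and reaction time are prespecified beside it

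*Combined protocol and SAP*

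**What the plan says.** Section 2 (Aim 3a) sets out to describe ALLO's effect on "response inhibition using the Go No-Go task", next to verbal memory. Section 5, B. Assessments, under Cognitive functioning, gives the task: "A series of rectangles are presented every 1150 ms", with a press required for one colour and withheld for the other. Participants are told "to give equal importance to speed and accuracy". The score is then fixed: "The primary outcome is the number of commission errors".

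No other Go/No-Go score appears in the protocol or in section 5, D (Data analysis). Go-trial omissions, go reaction time, a sensitivity or bias index, and a rule for a participant who stops responding are all absent. Trial counts, the go to no-go ratio and the response window are not given either.

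On sedation, section 3-4 (Proposed study) states that at the study doses "ALLO is very well tolerated with mild sedation being the main side effect". The sample-size paragraph rests its effect size on earlier reports of a large ALLO effect (d above 0.8) "on saccadic eye movement and sedation among healthy subjects". Section 6.1 lists sedation and alcohol-like intoxication among the common effects.

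Table 2 in section 6 schedules Go/No-Go at baseline, -40, +90 and +150 minutes. At +90 and +150 the battery reads "STAI-6, VAS, BAES, NDS, ARCI, SDAS, HVLT-R, Go no-Go, Grooved Pegboard".

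**The concern.** A commission error is a press on a no-go trial. Its count falls if inhibition improves. It also falls if the participant presses less overall, through drowsy lapses, or slows down enough to withhold more easily. The plan expects sedation from ALLO, and only one arm receives ALLO. Any such shift is a treatment effect on responding, so randomisation does not remove it from the comparison. The instruction balances speed against accuracy, but the named score records neither speed nor missed go trials.

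At stake is what Aim 3a can say. An unchanged or lower count on ALLO could be reported as preserved or better inhibition when it reflects fewer presses. The background prepares a reader for that reading: it cites a study in cocaine-dependent people in which higher ALLO went with better cognition.

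**Working it through.** **The plan's own figure.** The document gives no power or effect figure for Go/No-Go. Its general ALLO-placebo figure is d = 0.74 with 30 per group, 80% power and alpha 0.05. A two-sided two-sample t-test gives power 0.805 at d = 0.74, and solving for 80% power gives d = 0.736. The figure reproduces, so sample size is not the issue.

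**Inputs.** Commission, omission and lapse rates are not in the documents. Everything below is assumed and illustrative.

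**1. Lapse model.** Let c be the commission rate and h the hit rate on attended trials, and L the share of all trials on which a sedated participant makes no response.

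- Observed commissions = (1 - L)c
- Observed omissions = 1 - (1 - L)h
- d' = z(hits) - z(commissions)

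With c = 20%, h = 98% and attended-trial inhibition unchanged:

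| L | Commissions | Omissions | d' |
|---|---|---|---|
| 0 | 20.0% | 2.0% | 2.90 |
| 5% | 19.0% | 6.9% | 2.36 |
| 10% | 18.0% | 11.8% | 2.10 |
| 20% | 16.0% | 21.6% | 1.78 |

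The commission count improves slightly although inhibition has not changed.

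**2. How much true worsening is hidden.** If attended-trial commissions rise by a relative amount r, the observed rate is (1 - L)(1 + r)c. It equals c when r = L/(1 - L):

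- L = 5%: 0.05/0.95 = 5.3%
- L = 10%: 0.10/0.90 = 11.1%
- L = 20%: 0.20/0.80 = 25%

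This does not depend on c.

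**3. What a sign reversal requires.** For a true rise of r = 10%, commissions fall below baseline only if L exceeds 0.10/1.10 = 9.1%. Omissions then exceed 1 - 0.909 x 0.98 = 10.9%, against 2% unsedated.

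An equal-variance signal-detection model gives a similar message. Start at d' = 2.5 with 20% commissions, so hits are Phi(2.5 - 0.842) = 95.1%. Let d' fall to 2.0, so commissions = Phi(z(hits) - 2.0):

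| Hits | Commissions |
|---|---|
| 95% | 36.1% |
| 92% | 27.6% |
| 90% | 23.6% |
| 85% | 16.8% |
| 80% | 12.3% |

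The crossover is at hits = Phi(2.0 - 0.842) = 87.7%, so omissions must rise from about 5% to above 12.3%. With smaller losses of hits the count worsens, as it should.

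**4. Simulation.** The assumptions were 30 per arm, 50 no-go and 200 go trials, baseline commissions of 10%, 20% or 30%, mean lapses of 10% or 20%, and a true 10% relative rise in commissions. There were 2,000 runs per setting, tested at unadjusted two-sided 0.05. The commission count showed ALLO significantly worse in 0.2% to 2.4% of runs and significantly better in 2.8% to 12.8%. Chance alone would give 2.5% each way. A difference in omissions was detected in every run, and one in d' in at least 99.95%. The usual result of the commission test is therefore a null, not a significant wrong sign.

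Slowing was not modelled, because the response window is not stated.

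**The case against.** The strongest reply is that the plan already measures sedation. HVLT-R, Grooved Pegboard, BAES and VAS are taken at all four Go/No-Go times, and plasma ALLO is to be related to cognitive performance. General impairment would probably be seen. That stands, and it limits the point to the inhibition score. It does not remove the point: none of those measures assesses inhibition, and section 5, D does not link them to the Go/No-Go result.

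Second, a shift in responding is not certain. The sedation expected is mild. The only Go/No-Go test on ALLO without alcohol is at -40 minutes, 20 minutes into the infusion and before the 60 minutes after which section 2 expects levels to stabilise. Both arms receive alcohol, and section 6.1 anticipates that ALLO will blunt alcohol's effects. Impaired inhibition could also outweigh lapses and raise the count. All of this stands, and it is why direction and size are left open.

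Third, naming a primary outcome for the task does not forbid other scores. True, but none is prespecified, and adding them after seeing the data carries less weight.

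A reader might infer that d' should replace commission errors. The working does not support that: d' falls from 2.90 to 2.10 with 10% lapses and unchanged inhibition, so it reports inattention as poorer discrimination. It also does not record speed.

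**Conclusion.** The gap is real but modest. As specified, a lower or unchanged commission count on ALLO cannot be attributed to response inhibition, because reduced responding gives the same result and is not scored. Under the assumed lapse model, lapses on 5% to 20% of trials hide a relative rise of about 5% to 25% in commissions. These figures rest on assumed rates and show what is possible, not what will happen.

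Two stronger readings are tempting. One is that the Aim 3a result will have the wrong sign. The documents give no task data to support that, and reversal needs omissions to rise to more than about 11% to 12% in the examples above. The other is that impairment under ALLO with alcohol would be missed altogether. The other measures taken at the same times make that unlikely.

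Aim 3a is secondary and descriptive. The primary testing rule ("All statistical testing for the primary hypotheses will be two-sided at 0.05 significance level") and the primary aims are unaffected. This is a change to consider, not a required correction.

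**What to change.** - Keep commission errors as the Go/No-Go outcome.
- Prespecify go-trial omission rate and mean go reaction time, reported by arm and time point.
- State the reading rule: fewer or unchanged commission errors on ALLO count as better or preserved inhibition only if omissions and go reaction time are not worse on ALLO. Judge this on estimates with confidence intervals, since a non-significant difference at 30 per arm does not show that nothing worsened.
- Optionally add d' as a supportive score, with a stated correction for rates of 0 or 1.

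The scores come from the same key presses, so no new procedure, visit or participant is needed. The cost is analysis wording and two more secondary descriptive scores. If those are formally tested, the Bonferroni family for secondary outcomes grows slightly; the plan does not state its present size.
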